#### Follow-Up of Abnormal Laboratory Test Values

In the event of medically significant unexplained abnormal laboratory test values, the tests should be repeated and followed up until they have returned to the normal range and/or an adequate explanation of the abnormality is found. If a clear explanation is established, it should be recorded on the Adverse Event eCRF.

During the study conduct, investigators notified of a patient's critical laboratory test (Section 4.3.6 criteria for re-treatment with ocrelizumab) result will be instructed to suspend further treatment with study drug until the patient can be further evaluated. A repeat laboratory test may be necessary to confirm the results. Patients with values below these critical values should not be re-treated until the re-treatment criteria are met, and these laboratory values have normalized.

# 5.3.5.7 Abnormal Vital Sign Values

Not every vital sign abnormality qualifies as an adverse event. A vital sign result must be reported as an adverse event if it meets any of the following criteria:

- Is accompanied by clinical symptoms
- Results in a change in study treatment (e.g., dosage modification, treatment interruption, or treatment discontinuation)
- Results in a medical intervention or a change in concomitant therapy
- Is clinically significant in the investigator's judgment

It is the investigator's responsibility to review all vital sign findings. Medical and scientific judgment should be exercised in deciding whether an isolated vital sign abnormality should be classified as an adverse event.

If a clinically significant vital sign abnormality is a sign of a disease or syndrome (e.g., high blood pressure), only the diagnosis (i.e., hypertension) should be recorded on the Adverse Event eCRF.

Observations of the same clinically significant vital sign abnormality from visit to visit should only be recorded once on the Adverse Event eCRF (see Section 5.3.5.5, for details on recording persistent adverse events).

If a clinically significant vital sign abnormality is observed during the infusion of ocrelizumab, the event should be reported on a dedicated Adverse Event eForm, prespecified Infusion-Related Reaction. Associated signs and symptoms, including severity, should be recorded on this dedicated Infusion-Related Reaction eForm (see Section 5.3.5.1). Observation of the same significant vital sign abnormality at any subsequent infusion should be recorded on a dedicated prespecified Infusion-Related Reaction Related Reaction eForm.

# 5.3.5.8 Abnormal Liver Function Tests

The finding of an elevated ALT or AST (> $3 \times ULN$ ) in combination with either an elevated total bilirubin (> $2 \times ULN$ ) or clinical jaundice in the absence of cholestasis or other causes of hyperbilirubinemia is considered to be an indicator of severe liver injury (as defined by Hy's Law). Therefore, investigators must report as an adverse event the occurrence of either of the following:

- Treatment-emergent ALT or AST  $> 3 \times ULN$  in combination with total bilirubin  $> 2 \times ULN$
- Treatment-emergent ALT or AST  $> 3 \times ULN$  in combination with clinical jaundice

The most appropriate diagnosis or (if a diagnosis cannot be established) the abnormal laboratory values should be recorded on the Adverse Event eCRF and reported to the Sponsor immediately (i.e., no more than 24 hours after learning of the event), either as a serious adverse event or an adverse event of special interest (see Section 5.4.1).

# 5.3.5.9 Deaths

All deaths that occur during the protocol-specified adverse event reporting period (see Section 5.3.1), regardless of relationship to study drug, must be recorded on the Adverse Event eCRF and immediately reported to the Sponsor (see Section 5.4.1). This includes death attributed to progression of MS.

Death should be considered an outcome and not a distinct event. The event or condition that caused or contributed to the fatal outcome should be recorded as the single medical concept on the Adverse Event eCRF. Generally, only one such event should be reported. If the cause of death is unknown and cannot be ascertained at the time of reporting, **"unexplained death"** should be recorded on the Adverse Event eCRF. If the cause of death later becomes available (e.g., after autopsy), "unexplained death" should be replaced by the established cause of death. The term **"sudden death"** should not be used unless combined with the presumed cause of death (e.g., "sudden cardiac death").

If the death is attributed to progression of MS, "multiple sclerosis progression" should be recorded on the Adverse Event eCRF.

Ocrelizumab—F. Hoffmann-La Roche Ltd 103/Protocol WA39085, Version 10 Deaths that occur after the adverse event reporting period should be reported as described in Section 5.6.

# 5.3.5.10 Preexisting Medical Conditions

A preexisting medical condition is one that is present at the screening visit for this study. Such conditions should be recorded on the General Medical History and Baseline Conditions eCRF.

A preexisting medical condition should be recorded as an adverse event only if the frequency, severity, or character of the condition worsens during the study. When recording such events on the Adverse Event eCRF, it is important to convey the concept that the preexisting condition has changed by including applicable descriptors (e.g., "more frequent headaches").

# 5.3.5.11 Lack of Efficacy or Worsening of Multiple Sclerosis

Events that are clearly consistent with the expected pattern of progression of the underlying disease should not be recorded as adverse events. Clinical relapses should be captured on the MS Relapse eForm (see Section 5.2.1,). These data will be captured as exploratory assessment data only. However, every effort should be made to document progression through use of objective criteria. If there is any uncertainty as to whether an event is due to disease progression, it should be reported as an adverse event.

Medical occurrences or symptoms of deterioration that are judged by the investigator to have unexpectedly worsened in severity or frequency or changed in nature at any time during the study should be recorded as an adverse event.

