# 4.5.15 Neurologic Examination

A neurologic examination should be performed at every planned visit and unscheduled visit if applicable.

In the presence of newly identified or worsening neurologic symptoms at any given time in the study, a neurologic evaluation should be scheduled promptly. In case of events suggestive of relapse, the EDSS assessment (see Section 4.5.14) is to be performed within 7 days of the onset of the relapse. If the relapse is confirmed, it will be reported on the prespecified MS Relapse eCRF. In case the relapse is not confirmed, an adverse event will be reported as applicable.

Study investigators will screen patients for signs and symptoms of PML by evaluating neurologic deficits localized to the cerebral cortex, such as cortical symptoms/signs, behavioral and neuropsychological alteration, retrochiasmal visual defects, hemiparesis, and cerebellar symptoms/signs (e.g., gait abnormalities, limb incoordination; see Section 5.1.1.3 for more information). A brain MRI scan and CSF analysis may be warranted to assist in the diagnosis of PML. See Appendix 5 for guidance on the diagnosis of PML.

Patients with suspected PML, which necessitates MRI and/or lumbar puncture and CSF analyses to rule out PML, should be withheld from study treatment until PML is ruled out by complete clinical evaluation and appropriate diagnostic testing (see Appendix 5). The Sponsor's Medical Monitor should be immediately contacted (see Section 5.4.1).

A patient with confirmed PML should be withdrawn from treatment. PML should be reported as a serious adverse event (with all available information) with immediate notification of the Sponsor's Medical Monitor (see Section 5.4.1).

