# 5.2.1 Adverse Events

According to the ICH guideline for Good Clinical Practice, an adverse event is any untoward medical occurrence in a clinical investigation subject administered a pharmaceutical product, regardless of causal attribution. An adverse event can therefore be any of the following:

• Any unfavorable and unintended sign (including an abnormal laboratory finding), symptom, or disease temporally associated with the use of a medicinal product, whether or not considered related to the medicinal product

- Any new disease or exacerbation of an existing disease (a worsening in the character, frequency, or severity of a known condition), except as described in Section 5.3.5.11
- Recurrence of an intermittent medical condition (e.g., headache) not present at baseline
- Any deterioration in a laboratory value or other clinical test (e.g., ECG, X-ray) that is associated with symptoms or leads to a change in study treatment or concomitant treatment or discontinuation from study drug
- Adverse events that are related to a protocol-mandated intervention, including those that occur prior to assignment of study treatment (e.g., screening invasive procedures such as biopsies)

New or worsening neurologic symptoms not considered MS-related should be recorded on an Adverse Event eCRF, and the Medical Monitor should be informed.

Adverse events will be recorded on the Adverse Event eCRF. For clinical relapses and IRRs, a Specific Adverse Event eCRF triggered by an appropriate entry on the main Adverse Event eCRF will be used. The reporting requirements will be the same as for any other adverse event.

Further information related to clinical relapses will be recorded only on a prespecified eCRF MS Relapse eCRF. Signs, symptoms, and severity of IRRs will also be recorded on a prespecified IRR eCRF.

B-cell depletion is the expected outcome of ocrelizumab treatment and is not an adverse event. However, patients may be at risk for infections, and particular attention should be directed toward early identification and treatment of infections (see Section 5.1.1.2).

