#### 5.2.2 Serious Adverse Events (Immediately Reportable to the Sponsor)

A serious adverse event is any adverse event that meets any of the following criteria:

- Is fatal (i.e., the adverse event actually causes or leads to death)
- Is life threatening (i.e., the adverse event, in the view of the investigator, places the patient at immediate risk of death)
- This does not include any adverse event that, had it occurred in a more severe form or was allowed to continue, might have caused death.
- Requires or prolongs inpatient hospitalization (see Section 5.3.5.12)
- Results in persistent or significant disability/incapacity (i.e., the adverse event results in substantial disruption of the patient's ability to conduct normal life functions)
- Is a congenital anomaly/birth defect in a neonate/infant born to a mother exposed to study drug

Ocrelizumab—F. Hoffmann-La Roche Ltd 96/Protocol WA39085, Version 10 • Is a significant medical event in the investigator's judgment (e.g., may jeopardize the patient or may require medical/surgical intervention to prevent one of the outcomes listed above)

The exception to this definition of a serious adverse event is in the event that a patient is hospitalized following an MS relapse, as long as the reason for hospitalization is to receive standard treatment with IV methylprednisolone. The rationale for this exception is that some countries and/or clinical sites routinely hospitalize patients who require administration of methylprednisolone in the event of an MS relapse. Thus, the serious adverse event criteria for "hospitalization" would be met on the basis of local practice and would not reflect the seriousness of the event.

When the MS relapse results in hospitalization for any reason other than for routine treatment of the relapse (such as for a treatment course beyond the standard treatment) or when hospitalization is prolonged, the MS relapse should be considered a serious adverse event.

The terms "severe" and "serious" are not synonymous. Severity refers to the intensity of an adverse event (e.g., rated as mild, moderate, or severe, or according to National Cancer Institute Common Terminology Criteria for Adverse Events [NCI CTCAE]; see Section 5.3.3); the event itself may be of relatively minor medical significance (such as severe headache without any further findings).

Severity and seriousness need to be independently assessed for each adverse event recorded on the eCRF.

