# 5.3.5.2 Clinical Relapses

Further information related to clinical relapses will be recorded on a prespecified MS Relapse eForm, which will be triggered by an appropriate response on the main Adverse Event eForm.

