#### 6.6 SAFETY ANALYSES

Safety data will be listed individually and summarized descriptively by cohort/dose level for the Dose Exploration period and the OOE. The exposure period (time at risk) for each safety endpoint is defined as time from the date of the first exposure to the study treatment to the date of study withdrawal or clinical cutoff date, whichever occurs earlier.

The safety endpoints include, but may not be limited to, the following:

- Incidence of adverse events (overall, by severity, and by relationship to study medication)
- Incidence of serious adverse events
- Incidence of treatment discontinuations due to adverse events
- Change from baseline by time in laboratory parameters and incidence of clinically significant laboratory abnormalities
- Change from baseline by time in vital signs (systolic blood pressure, diastolic blood pressure, pulse rate, respiratory rate, body temperature) and incidence of vital sign abnormalities

The incidence count for each adverse event will be defined as the number of patients reporting at least one treatment-emergent occurrence of the event. The incidence rate will be calculated as the incidence count divided by the total number of patients in each cohort as well as total. In addition, the rate per 100 patient-years (along with the 95% confidence interval using the exact method based on the Poisson distribution) will be calculated for all adverse events and serious adverse events.

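### Sections conflict on whether a non-serious MS relapse is an adverse event, so the Section 6.6 AE rate can depend on site reading and local hospitalization practice

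*Combined protocol and SAP*

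**What the plan says.** Three sections treat a relapse as an AE.

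- Section 5.2.1: "For clinical relapses and IRRs, a Specific Adverse Event eCRF triggered by an appropriate entry on the main Adverse Event eCRF will be used", followed by "The reporting requirements will be the same as for any other adverse event".
- Section 5.3.5.2 places further relapse detail on the MS Relapse form, "which will be triggered by an appropriate response on the main Adverse Event eForm".
- Section 5.3.5.3 exempts relapse from the rule of recording a diagnosis instead of symptoms, and in doing so lists it among adverse events.

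Three sections point the other way.

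- Section 5.3.5.11 keeps expected disease progression off the AE form, sends clinical relapses to the MS Relapse form with a reference back to 5.2.1, and adds: "These data will be captured as exploratory assessment data only".
- Section 4.5.15 sends a confirmed relapse to the MS Relapse form, then says: "In case the relapse is not confirmed, an adverse event will be reported as applicable".
- Section 5.3.5.12 lists hospitalization for standard IV methylprednisolone after a relapse among the circumstances reported neither as an AE nor as an SAE.

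The AE definition in 5.2.1 covers exacerbation of an existing disease "except as described in Section 5.3.5.11", so 5.2.1 and 5.3.5.11 refer to each other.

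Section 6.6 defines the incidence count as patients with at least one occurrence. It adds a rate per 100 patient-years with an exact Poisson 95% confidence interval, which "will be calculated for all adverse events and serious adverse events". It has no rule on relapses.

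**The concern.** Relapse is an exploratory endpoint in Table 1, and AE occurrence is a secondary safety endpoint. If the same event can be recorded as an AE at one site and as exploratory data at another, part of the AE numerator reflects how the protocol was read and not what happened to patients. Section 5.3.5.12 adds a second dependence. Two patients with the same relapse and the same steroid course could be counted differently because one hospital admits for the infusion and the other does not. The protocol acknowledges that admission practice varies by country and site. The affected rate carries the only confidence interval specified in Section 6.

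**Working it through.** **Setting the sections side by side.** Take a confirmed relapse that meets no seriousness criterion and is treated with standard IV methylprednisolone.

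| Rule followed | Treated as outpatient | Admitted for the infusion |
|---|---|---|
| 5.2.1, 5.3.5.2, 5.3.5.3 | AE | AE |
| 5.3.5.11, if the restriction covers the event itself | Not an AE | Not an AE |
| 4.5.15 | Relapse form; no AE named | Relapse form; no AE named |
| 5.3.5.12, literally | Not addressed | Neither AE nor SAE |

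A site applying 5.2.1 together with 5.3.5.12 counts the outpatient case and drops the inpatient one. The reason printed in 5.3.5.12 concerns only the hospitalization criterion for seriousness. It does not explain why AE status should go as well.

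**SAE rule.** Section 5.2.2 excludes admission for routine steroid treatment. It says that with any other, or prolonged, hospitalization "the MS relapse should be considered a serious adverse event". Section 5.3.5.12 repeats the exclusion, and 5.4 lists serious relapse among events to be reported within 24 hours. These agree.

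**Size of the AE effect.** The plan states no AE or relapse rate to reproduce, so this is an illustration.

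Inputs from the documents: 4194 AEs in 825 ocrelizumab patients over 96 weeks (1.2.4.2); 12 to about 36 patients (3.1.1); 402 weeks of participation (3.3). The last figure reproduces as 10 + 24 + 264 + 104 = 402, leaving 392 weeks after a 10-week screening. Assumption: 0.05 to 0.30 relapses per patient-year, with 0.1 to 0.5 as a wider alternative.

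- Adult scale: 825 × 96 × 7 / 365.25 = 1518 patient-years; 4194 / 1518 = 276 per 100 patient-years. Full exposure is assumed, so the true adult rate is at least this and the percentage shifts below are, if anything, too large.
- Relative shift = relapse rate / AE rate, whatever the exposure: 5/276 = 1.8%; 10/276 = 3.6%; 30/276 = 10.9%; 50/276 = 18.1%.
- 12 patients: 12 × 392 × 7 / 365.25 = 90.2 patient-years.

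| Numerator, 12 patients | Events | Rate per 100 patient-years | Exact 95% CI |
|---|---|---|---|
| Without relapses | 249 | 276 | 243 to 313 |
| With relapses at 0.05 per year | 249 + 5 = 254 | 282 | 248 to 319 |
| With relapses at 0.30 per year | 249 + 27 = 276 | 306 | 271 to 345 |

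In whole events the shift is 5/249 = 2.0% to 27/249 = 10.8%.

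- 36 patients: 270.5 patient-years; 747 events without relapses, 276 (257 to 297); with relapses at 0.30 per year, 747 + 81 = 828 events, 306 (286 to 328).

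**The case against.** The strongest reply is that the text can be reconciled: the AE-form entry counts as an AE, and only the extra detail on the MS Relapse form is exploratory. This has support. Section 5.3.5.11 treats progression and relapse in separate sentences. Sections 5.2.1 and 5.3.5.2 speak of further information going to the relapse form. Section 5.3.5.3 classes relapse as an AE, and 4.5.3.4 gives completion of both forms as an example. If the relapse form opens only from an AE entry, sites have little discretion. But the protocol never states this reading. Section 4.5.15 sits badly with it, and 5.3.5.12 contradicts it for admitted patients.

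The practical limits stand. All analyses are descriptive. With 12 patients, even 306 lies inside the no-relapse interval of 243 to 313. Incidence counted per patient is less sensitive, since an added relapse changes nothing in a patient who already has an AE. AEs are listed individually and summarized by mapped term, so relapses that were entered could be subtracted by hand. That does not recover relapses kept off the AE form. That sites actually differ is a possibility created by the text, not an observed fact.

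Two stronger readings are tempting. A reader might infer that the SAE rate also has two possible numerators. The documents do not support this: 5.2.2, 5.3.5.12 and 5.4 agree, and only the word *only* in 5.3.5.11, read as overriding them, would disturb that rule. A reader might also infer that counting relapses spoils comparison with the adult AE figures. The documents do not say whether the adult count included relapses, and the planned bridging to adults rests on exposure and B-cell depletion, not AE rates.

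**Conclusion.** The point holds for non-serious relapses. The recording sections conflict, Section 6.6 does not settle the matter, and read literally the AE count can turn on local admission practice. For SAEs the rule is sound; what remains is to stop the restriction in 5.3.5.11 from appearing to cover serious relapses.

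The likely size is modest: about 2% to 11% of the AE rate at 0.05 to 0.30 relapses per patient-year, or 4% to 18% at 0.1 to 0.5. These ranges rest on assumed relapse rates and on an adult AE rate used only for scale. The shift stays within the no-relapse interval for 12 patients up to 0.30 per year. With 36 patients at that rate, 306 lies above the upper limit of 297. No hypothesis test or conclusion of the study turns on it, but it affects the only interval estimate planned and is easily removed.

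**What to change.** - Reconcile 4.5.15, 5.2.1, 5.3.5.2, 5.3.5.11 and 5.3.5.12 into one recording rule for clinical relapses that does not depend on whether the patient is admitted for steroids, and keep 5.3.5.3 in line with it. In 5.3.5.12, leave the SAE exemption and let AE status follow the general rule.
- In 5.3.5.11, limit the exploratory-only statement to non-serious relapses or to the detail on the MS Relapse form.
- In 6.6, flag MS relapse terms and present AE incidence and the rate per 100 patient-years both with and without them. Showing both avoids a choice that the documents do not make. Removing relapses outright could drop serious ones.
- State in 6.6 that relapses serious under 5.2.2 always count in SAE incidence and the SAE rate.
- For relapses recorded under the current text, compare AE-form entries with the MS Relapse form, on which 4.5.13 requires every clinical relapse.

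The cost is a short text change, one dataset flag and one extra table row.

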# 5.3.5.12 Hospitalization or Prolonged Hospitalization

Any adverse event that results in hospitalization (i.e., inpatient admission to a hospital) or prolonged hospitalization should be documented and reported as a serious adverse event (per the definition of serious adverse event in Section 5.2.2), except as outlined below.

An event that leads to hospitalization under the following circumstances should not be reported as an adverse event or a serious adverse event:

- Hospitalization for respite care
- Planned hospitalization required by the protocol (e.g., for study drug administration or insertion of access device for study drug administration)
- Hospitalization for a preexisting condition, provided that all of the following criteria are met:

The hospitalization was planned prior to the study or was scheduled during the study when elective surgery became necessary because of the expected normal progression of the disease.

The patient has not experienced an adverse event.

- Hospitalization to receive trial medication, such as infusions of ocrelizumab, unless this is more than 24 hours
- Hospitalization for supervision purposes following completion of ocrelizumab infusion, when not associated with an adverse event
- Hospitalization to receive standard treatment with IV methylprednisolone following an MS relapse

The rationale for this exception is that some countries and/or clinical sites routinely hospitalize patients who require administration of methylprednisolone in the event of an MS relapse. Thus, the serious adverse event criteria for "hospitalization" would be met on the basis of local practice and would not reflect the seriousness of the event.

An event that leads to hospitalization under the following circumstances is not considered to be a serious adverse event, but should be reported as an adverse event instead:

• Hospitalization for an adverse event that would ordinarily have been treated in an outpatient setting had an outpatient clinic been available

